9.8 Quality control

The study will be conducted according to European Network of Centres for Pharmacoepidemiology and Pharmacovigilance (ENCePP) Guide on Methodological Standards in Pharmacoepidemiology, the ENCePP Checklist for Study Protocols, the International Society for Pharmacoepidemiology (ISPE) Good Pharmacoepidemiology Practice (GPP) Guidelines and IQVIA standard operating procedures. At the study level, all aspects of the study from protocol development to the reporting of the results will be conducted within the framework of the IQVIA Quality Management System.

According to the policies and procedures above, a Quality Control (QC) plan for the study will be developed and executed, which will include QC on the protocol in general, study methodology, SAP, programming, data management and analysis, and study report including study results and conclusions.

Furthermore:

- The study QC plan will establish ownership for the execution of the individual QC steps. The principle of the independence of QC applies.
- IQVIA project management will ensure that individuals responsible for the execution of specific QC steps will have knowledge, capability and experience which are adequate for the task.
- The result of the execution of the individual steps of the QC plan will be documented, and include the required corrective actions, if any.
- The execution of any required corrective action will be documented.
- Datasets and analytic programmes will be stored according to IQVIA and data holder procedures, with access restricted to authorised study personnel at the respective entities.

Also, the Project Manager of the study will verify training compliance of IQVIA employees contributing to the study, as per IQVIA procedure RWI_WI_PM0035 “Real World Project-Specific Training and Staff Transition”.

The executed QC plan will be subjected to a final review and approval for sufficiency and completeness by the IQVIA project management team.

9.9 Limitations of the research methods

Use of secondary data collected and maintained in electronic databases offers several scientific and operational advantages for conducting a pregnancy study, including specifically:

- The possibility of mitigating the information and selection bias that may affect primary data collection which involves a self-selected population of pregnant women and their infants.
- The opportunity to study all the eligible exposed and non-exposed pregnancies (i.e., no individual informed consent for this study is required) in women with SLE.
- The potential to optimise statistical efficiency with a 1:n (e.g., 1:3) match of exposed and non-exposed pregnancies.
- Additionally, national databases such as those from Nordic countries are known to be representative of the population of the country, typically containing lifetime data of patients and have demonstrably been used for research to obtain insights into the real-world use of pharmaceutical products. The presence of medical birth registries and registers of congenital malformation in some of these countries with high PPVs for adverse outcomes such as MCMs increases the internal validity of studies conducted using these national data sources.

The individual study databases have limitations typical of other real-world databases:

- Data are collected primarily for administrative purposes, so some medical information not directly related to reimbursement may be incomplete or not available at all. The accuracy of the available information may vary between data sources. This can affect the measurement of exposure to anifrolumab, the outcomes of interest and/or the covariates. To ensure that the accuracy of the retrieved information is acceptable, all data will be reviewed for possible inconsistencies or implausible information. Also, missing information may vary between data sources, and whenever applicable, missing information will be reported (please see Section 9.7).
- Information on all the study outcomes and individual covariates may not be available in all databases, in particular lifestyle variables and the up to 1-year assessment of growth of the infant.
- For some of the data sources, relatively long lag times must be considered, and these would vary by country. Thus, an assumption of a data lag time of approximately 2 years will be implemented.
- This study relies on data sources not primarily collected to conduct pregnancy outcomes studies. Accordingly, outcome misclassification due to limitations in sensitivity or specificity for the study outcomes cannot be ruled out. If this misclassification is non-differential between the exposed and unexposed cohorts, this will likely lead to bias toward the null and attenuate any true effect. Bias in other directions remains a possibility. On the

other hand, if misclassification is differential between exposed and unexposed cohorts, bias can affect the results in any direction.

- An exhaustive list of codes will be used to maximise the capture of non-live births. However, early spontaneous abortions, which usually occur in the first 6 weeks of gestation, are not commonly recorded, and this may introduce outcome misclassification. As the included women are patients with moderate/severe SLE who may more often seek medical advice due to their condition and to the SLE-related increased risk of spontaneous abortion, the misreporting of spontaneous abortions is expected to be low.
- Additionally, the likelihood that spontaneous abortions would be recorded differently in the data sources across exposed and unexposed cohorts is low. The net effect of this non-differential misclassification is a bias towards the null. As for the other adverse pregnancy outcomes, such as ectopic pregnancy or elective termination of pregnancy, these are likely to have a hospitalisation event associated, and as such, it is not likely that this would be differentially recorded in the exposed and unexposed cohorts.
- The definitions for spontaneous abortion and stillbirth vary by country. Whereas the definitions are uniform within Europe, they differ from those in the USA. As the occurrence of this outcome requires the use of ICD-10 codes recorded by individual data sources, further adjustments to harmonise the gestational age at event occurrence cannot be made.
- The definition of stillbirth includes both antepartum and intrapartum stillbirths, but they cannot be distinguished in the data and will be grouped for the purposes of analysis. However, most of the stillbirths will be antepartum (73). Rates of intrapartum stillbirth are not expected to be different between exposed and unexposed cohorts.
- For some data sources, there are reporting restrictions based on the overall number of events. For example, in Danish data sources, when the outcome for a specific analysis, has less than 5 cases/observations, the specific result and other potentially related results cannot be reported. This is because of the potential of patient identification. This may be a potential limitation for analyses that require stratifications, such as the exploratory analysis to investigate the risk of CM by target body system organ class or the risk of select pregnancy loss outcomes (composite of spontaneous abortion and stillbirth) by different pregnancy trimesters. In this instances, minimum and maximum values cannot be reported.

Also, some study analysis limitations must be acknowledged.

- Confounding by indication is common in comparative observational studies, and as the prescription of anifrolumab will depend on the assessment of the severity or activity of the disease, confounding by indication may occur. However, in this study, mitigation strategies, such as selection of only moderate/severe SLE cases has been planned to minimise the presence of confounding by indication. Furthermore, PS methods will be applied to minimise the potential for confounding due to differences in baseline characteristics between the exposed and unexposed groups.

- Regarding SLE SOC, the recordings of exposure based on prescription or dispensation alone do not guarantee that the patient ingested or injected the medication; the recordings of prescriptions are an expression of the treating physician's recommendation of the drug, and the prescriptions dispensed at community pharmacies and insurance claims registrations are an expression of the patients' intention to follow the recommendation from the physician.
- Considering the IV infusion as the current route of administration of anifrolumab, definition of exposure may be challenging. Outpatient visits with a recording of the relevant ATC and/or procedure codes, rather than the prescribing/dispensing records may be needed to determine the exposure status of study subjects. This could potentially lead to misclassification of the exposure (i.e., use of anifrolumab may be under-detected). Such a potential bias would move the measure of association towards the null, since the exposure status of the cohorts would not be fully established, and the cohorts of exposed and non-exposed pregnancies will therefore be more similar. The feasibility assessment was used to inform the selection of data sources to minimise the impact of this potential limitation.
- It is assumed that all prescribed drugs are filled and then taken by patients in a compliant manner. Non-compliance would result in misclassification of exposure and could cause an underestimation of the association between exposure and outcome.
- SLE severity and activity algorithms were adapted from a previously published algorithm used in other settings (50), including the data sources included in this study, to meet current criteria and recommendations of medication use in SLE patients. The assumptions made for the proposed adaptations were based on the experience of the study team, including database analysis expertise and clinical knowledge, but also on literature relevant to the subject, ensuring that sound assumptions are made.
- For some of the diagnoses included in the activity algorithm, distinguishing clinical manifestations (i.e., acute illnesses) that define active SLE from comorbidities may not be possible (e.g., renal impairment). Therefore, there is a possibility of misclassifying signs of active disease as a comorbidity. The impact of this misclassification is considered minimal as adjustments will be made for disease activity as well as disease severity.
- Since anifrolumab prescribing is not recommended in pregnancy, uptake of the drug in pregnancy may be extremely limited at least in the initial years of launch post-authorisation, thus hampering the feasibility of the safety analyses with respect to study size targets.
- Misclassification may occur in the derivation of date of conception. When based on LMP, the derivation of date of conception assumes an average cycle length of 28 days and that conception occurred mid-cycle. The LMP is also subject to accuracy of recall by the woman, regularity of her cycles, and variations in the interval between bleeding and anovulation. When based on gestational age, the degree of misclassification depends on the method and accuracy of the gestational age assessment. However, the misclassification is expected to be within a range of days for most patients.

- Immortal time bias cannot be ruled out. Immortal time is the period during which the outcome of interest cannot occur because of the study design (108). In this study, there is an immortal time because a pregnancy must “survive” until initiation of treatment to be considered as exposed. Nevertheless, it is expected that most pregnant women would have exposure to anifrolumab in the first trimester, and exposure to anifrolumab initiation in the second or third trimester is not expected to be frequent. Adding to this, most outcomes that terminate a pregnancy, such as a spontaneous abortion or an ectopic pregnancy, are expected to happen in the first trimester, thus minimising the impact of this bias.
- The probability of receiving anifrolumab may be related to the length of pregnancy, to some extent. The patients with longer pregnancies have more opportunity (i.e., time) to be prescribed anifrolumab, while the patients with shorter pregnancies have less opportunity (i.e., time) to be prescribed anifrolumab. This may cause a bias in the analysis as shorter pregnancies are more likely to be included in the study cohort unexposed to anifrolumab.
- Both maternal and paternal disease history can be important predictors of the risk of adverse pregnancy outcomes because of shared environmental and genetic risk factors. For this study, no paternal data will be available because linkage to paternal data is not possible for most data sources. Therefore, offspring whose fathers have a history of CM before pregnancy will not be excluded, and no adjustments can be made for potential confounders related to fathers.
- All relevant measured covariates will be entered into the PS and/or outcome regression models (comparative analyses in objectives 2, 4, 7, 9, 11, and 14). However, given that registries may not contain information on all relevant known and unknown confounding variables, residual confounding may still be present in the study results.

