9.5.1.1 Assumptions used for the sample size and power calculations

To estimate the number of anifrolumab exposed SLE pregnancies and the expected number of primary study outcome events in data sources that would be eligible for the analysis in this study, the following assumptions were used:

- **A prevalence of 7% for MCM outcome.** Prevalence of MCM in pregnancies in women with moderate-to-severe SLE was estimated based on a literature search. Among moderate/severe SLE patients exposed to belimumab, birth defect prevalence estimates of 5.6% to 21.7% were observed in post hoc summary of clinical studies and a prospective

pregnancy registry, respectively (86) A prevalence of 6.4% of congenital malformations was observed in renal SLE pregnancies (51) These proxy estimates of MCM in moderate-to-severe SLE align with the observed population based prevalence estimates ranging from 7.4% to 13.6% (114) among women diagnosed with SLE (117).

- **A prevalence of 20% for the composite of select pregnancy loss outcomes (composite of spontaneous abortion and stillbirth).** Prevalence of the composite outcome of select pregnancy loss (spontaneous abortion and stillbirth) in moderate-to-severe SLE pregnancies ranged from 15.3% to 30% (51, 81, 86). For the individual outcomes, the prevalence estimates ranged from 1.8% to 3.7% for stillbirths (51, 103, 120), and the prevalence estimate was 16% (12.1% to 19.9%) for spontaneous abortions (103). Based on the intended objective to evaluate embryo-foetal loss, a composite outcome of spontaneous abortion and stillbirth has been used.
- **Proportion of SLE pregnancies occurring in women with moderate-to-severe disease of 50%.** There is limited information on the proportion of SLE pregnancies that occur in women with moderate-to-severe disease. The proportion of moderate-to-severe disease at the time of diagnosis among the general SLE population is estimated to be 50% (66, 80). Literature regarding medication patterns for SLE pregnant women suggests that 40-45% use immunosuppressors and/or biologics, which may be a proxy indicator of moderate/severe disease (12, 67). Thus, in this study, an assumption of 50% was used.

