- **Proportion of unexposed to confirmed teratogenic SLE SOC and/or non-SLE SOC drugs of 80%.** It is estimated that 80% of the SLE pregnancies are not exposed to SLE SOC and non-SLE SOC confirmed teratogenic drugs before conception, with a time period of 5-half-lives of relevant drug (see list of confirmed teratogenic drugs and half-lives in Table 20), or during pregnancy. This estimate is based on the reported use of SLE SOC and/or non-SLE SOC drugs in SLE population (47, 48).
- **Proportion of anifrolumab exposure during the first trimester of pregnancy of 80%.** The majority of the anifrolumab exposed pregnancies are expected to be unplanned and exposed to anifrolumab only in the early stages of the pregnancy, as the current recommendations indicate that anifrolumab should only be used during pregnancy if the benefit outweighs the risk to the foetus (86). We therefore used the assumption that 80% of all anifrolumab exposed pregnancies are exposed to anifrolumab during the first trimester of pregnancy.
- **Proportion of anifrolumab exposed pregnancies in women with moderate-to-severe SLE of 5% and 10%.** Based on market forecasts, uptake of anifrolumab in the general SLE population is expected to grow from 5% within two years of market launch to 20% by 5 years after market launch. Given the uncertainty of how these forecasts apply to SLE women of child-bearing potential and to use in pregnant SLE women, we used a conservative lower bound (5%) and a more realistic midpoint value (10%) for the proportion of pregnancies in women with moderate-to-severe SLE exposed to anifrolumab.

In addition, to estimate the minimum required sample size and the expected power, the following assumptions were used:

- **Non-inferiority margin of RR of 2.5.** The RR of 2.5 was based on previously reported increase in risk of MCM for exposure to a major teratogenic drug (62).

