9.5.1.3 Methods for estimating required sample size and expected power

The required sample size and expected power calculations were based on the assumptions described above and were carried out separately for each primary outcome (MCM and select pregnancy loss) at the meta-analysis level. Data sources that had at least a 90% probability of having at least 1 event in each exposure group (see [Table 10](#) and [Table 11](#)) were included in the meta-analysis.

The sample size and power calculations were performed using simulations under the assumption that the true RR is 1.0. For both sample size and power calculations, simulations were repeated 1,000 times to get 1,000 simulated 95% CIs for RRs.

The required sample size to achieve 80% power for a one-sided alpha-level of 2.5% at meta-analysis were performed using simulations as detailed below:

1. For a given overall sample size, a proportion of the overall population was assigned to each of the data sources likely to be included in the meta-analysis (proportions are presented in [Table 12](#)).
2. The number of primary outcome events in each exposure group were randomly drawn for each data source from a binomial distribution. In the binomial distribution, the number of trials was set equal to the estimated data source-level sample size and the probability of success was set to equal to the prevalence of the outcome in each exposure group, assuming that the true RR is 1 (no effect of exposure).
3. The estimated data source level log(RRs), their standard errors, and their 95% CIs were computed using a log-link Poisson regression (in place of log-binomial regression which tended to not converge) from the simulated number of events.
4. The data source level log(RRs) and their standard errors were entered in a fixed-effect meta-analysis model where pooled 95% CIs were computed. The inverse-variance method was used for the meta-analysis. The meta-analysis was run using the meta package in R ([97](#)).
5. The steps 2-4 were repeated for 1,000 times, and the proportion (which represents the achieved power) of the 1,000 simulated 95% CI upper bounds that were smaller than the target RR of 2.5 was computed.
6. The overall sample size was varied to range over positive integers for simulations, and the required sample size for this study was identified as the minimum overall sample size necessary to achieve 80% power (as defined in step 5).

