9.5.2 Required sample size

The required total sample size was estimated as the minimum sample size necessary to achieve 80% power for a one-sided alpha-level of 2.5% at meta-analysis level to rule out a target threshold RR of 2.5 for each primary outcome (MCM and select pregnancy loss outcomes). The minimum sample size per data source was calculated based on the expected percentage that the data source would contribute to the total sample size in the meta-analysis (Table 12).

For MCM analysis, a total number of 630 live and non-live births (210 anifrolumab and 420 comparator) using a matching ratio of 1:2, or 732 live and non-live births (183 anifrolumab and 549 comparator) using a matching ratio of 1:3 would be required to achieve at least 80% power to rule out an RR of 2.5 or greater. For the select adverse pregnancy loss outcomes analysis, a total number of 216 pregnancies (72 anifrolumab and 144 comparator) using a matching ratio of 1:2, or 244 pregnancies (61 anifrolumab and 183 comparator) using a matching ratio of 1:3 would be necessary to achieve at least 80% power to rule out an RR of 2.5 or greater.

Table 12: Data source level sample size percentages and required sample sizes assuming that only USA (Carelon Research), USA (DAPI) and France contribute to the meta-analysis of the primary outcomes.

Data source	Percentage of the total sample size in the data sources for select pregnancy loss outcomes analysis ^a	Required sample size per anifrolumab exposure group for meta-analysis of the select pregnancy loss outcomes		Percentage of the total sample size in the data sources for MCM analysis ^a	Required sample size per anifrolumab exposure group for meta-analysis of MCM	
		1:2 matching ratio	1:3 matching ratio		1:2 matching ratio	1:3 matching ratio
USA (Carelon Research)	35%	25	21	31%	66	57
USA (DAPI)	35%	25	21	35%	73	64
France	30%	22	19	34%	71	62
In Total	100%	72	61	100%	210	183

^a Based on the estimated number of pregnancies in women with moderate/severe SLE eligible for the analysis and exposed to anifrolumab, as shown in Table 10 and Table 11.

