The rationale of this sensitivity analysis is to examine the robustness of the primary study outcome (MCM and select pregnancy loss outcomes) analysis results to unmeasured confounding. Quantitative bias analysis methods will be used for studying the effect of unmeasured confounding on the study results (68). The quantitative bias analysis methods will be selected depending on what is known about the potential unmeasured confounder and its relationship between the exposure and the primary study outcomes (26). If the effect of a specific confounder and its relationship between the exposure and the primary study outcomes is well understood, a simple equation may be used for quantifying the confounder's relationship to exposure and primary study outcomes. This method allows to estimate the primary study outcome analysis results after adjusting for the specific unmeasured confounder (26). This approach could be considered in cases where a specific confounder is measured in some but not all data sources (listed as a limitation in Section 9.9). In case nothing is known about a potential unmeasured confounder, methods such as the E-value approach may be considered (26). The E-value approach aims to assess how strongly an unmeasured confounder would have to be related to anifrolumab exposure and primary study outcomes to explain away (i.e., nullify) the observed association of anifrolumab exposure with the primary study outcomes (112). Further details on the methods will be provided in the SAP.

Account for actual use of SLE SOC during pregnancy

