9.3.2	Outcomes? (e.g. International Classification of Diseases (ICD), Medical Dictionary for Regulatory Activities (MedDRA))				9.4 Appendix C
9.3.3	Covariates and other characteristics?				9.4 Appendix C
9.4	Is a linkage method between data sources described? (e.g. based on a unique identifier or other)				9.4

Comments:

Separate subsections for each country.

Section 10: Analysis plan		Yes	No	N/A	Section Number
10.1	Are the statistical methods and the reason for their choice described?				9.7.1
10.2	Is study size and/or statistical precision estimated?				9.5
10.3	Are descriptive analyses included?				9.7.1
10.4	Are stratified analyses included?				
10.5	Does the plan describe methods for analytic control of confounding?				9.7.1
10.6	Does the plan describe methods for analytic control of outcome misclassification?				9.7.5
10.7	Does the plan describe methods for handling missing data?				9.7
10.8	Are relevant sensitivity analyses described?				9.7.5

Comments:

--

Section 11: Data management and quality control	Yes	No	N/A	Section Number
11.1 Does the protocol provide information on data storage? (e.g., software and IT environment, database maintenance and anti-fraud protection, archiving)				9.6
11.2 Are methods of quality assurance described?				9.8

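### Judging an RR of 2.5 on coded MCM leaves the acknowledged bias towards the null working in favour of the safety conclusion, and no planned analysis examines it

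*Protocol*

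**What the plan says.** Section 9.5.1.1 sets a "Non-inferiority margin of RR of 2.5". Section 9.5.2 sizes the study for "80% power for a one-sided alpha-level of 2.5% at meta-analysis level to rule out a target threshold RR of 2.5", and section 9.5.1.3 counts success as a pooled 95% upper limit below 2.5. Those simulations draw events directly at the assumed prevalence, with no term for sensitivity or specificity.

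Under section 9.3.2, MCM is identified by a recorded diagnosis code. Section 9.9 says that limits in sensitivity or specificity cannot be excluded. If the resulting error is non-differential, "this will likely lead to bias toward the null and attenuate any true effect"; the same item leaves other directions open.

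Section 9.7.5 plans a bias analysis for confounding: "Quantitative bias analysis methods will be used for studying the effect of unmeasured confounding on the study results". Its only item on outcome definition is the MACDP re-classification. Item 10.6 of the ENCePP checklist (Appendix B) asks "Does the plan describe methods for analytic control of outcome misclassification" and is answered Yes, with 9.7.5 as the reference.

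**The concern.** In a study looking for a difference, bias towards the null is usually the cautious direction. Here the favourable conclusion comes from an upper bound, so a pull towards 1 brings that bound down and is anti-conservative. Section 9.9 records the bias as a general limitation without noting that it helps the main safety conclusion.

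False-positive codes are what matter. Section 9.9 does credit some registers with high PPVs, with the Nordic databases as its example, but section 9.5.3 expects the pooled MCM analysis to rest on Carelon, DAPI and France only. Section 9.4.1.5 says Optum can access medical records to confirm outcomes, yet no confirmation of MCM is scheduled. A reader of checklist item 10.6 would think the matter was handled in 9.7.5.

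**Working it through.** **Inputs from the protocol.** Margin RR 2.5; one-sided 2.5%; MCM prevalence 7%; allocation 1:2. Exposed numbers are 102 + 114 + 116 = 332 at 10% uptake (Table 11) and 51 + 56 + 58 = 165 at 5% uptake (Table 10). Source-level log RRs are pooled by fixed-effect inverse variance.

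**Inputs not in the protocol (assumed).** Non-differential error; coded comparator risk held at 7%; comparator PPV from 100% down to 70%; sensitivity 1 unless stated.

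**Standard error.** Two forms were used, for a exposed and c comparator events out of n1 and n0. The Poisson form √(1/a + 1/c) matches section 9.5.1.3. The binomial form √(1/a − 1/n1 + 1/c − 1/n0) is closer to the log-binomial or robust Poisson model of section 9.7.1. Ranges below run from Poisson to binomial.

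**Reproducing the plan's figures** ("performed using simulations under the assumption that the true RR is 1.0"; Poisson form). Power is 80.2% at 210 exposed, 1:2 (protocol: 80%). At 332 exposed it is 96% for 1:2 and 98% for 1:3 (protocol: 96% and 98%). At 165 exposed, 1:2, it is 66–69% (protocol: 69%).

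**Coded RR when the true RR is 2.5.** With comparator PPV = v:
- true comparator risk t0 = 0.07v
- false-positive probability f = 0.07(1 − v)/(1 − t0)
- true exposed risk t1 = 2.5·t0
- coded exposed risk = t1 + (1 − t1)f; dividing by 0.07 gives the coded RR

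Example, v = 0.90: t0 = 0.063; f = 0.007/0.937 = 0.00747; t1 = 0.1575; coded exposed risk = 0.1575 + 0.8425 × 0.00747 = 0.1638; coded RR = 0.1638/0.07 = 2.34.

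**Probability that the pooled upper bound is below 2.5 when the true RR is 2.5** (1:2, one million repeats per cell):

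| PPV | Coded RR | 332 exposed (10% uptake) | 165 exposed (5% uptake) |
|---|---|---|---|
| 100% | 2.50 | 1.7–2.3% | 1.5–2.0% |
| 95% | 2.42 | 2.6–3.4% | 2.0–2.7% |
| 90% | 2.34 | 3.9–5.0% | 2.7–3.6% |
| 80% | 2.18 | 8.1–9.9% | 4.6–5.9% |
| 70% | 2.03 | 15–18% | 7.6–9.5% |

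**Missed cases only.** With specificity 1 and true comparator risk 7%, sensitivity of 0.8 or 0.6 leaves the RR at 2.5 and the error at about 1.8–2.3% (332 exposed).

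**Both errors.** Sensitivity 0.8, specificity 0.99, true comparator risk 7%: coded risks are 0.056 + 0.0093 = 0.0653 and 0.14 + 0.00825 = 0.14825, so the coded RR is 2.27 and the error is 5.3–6.6% (332 exposed).

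Below PPV 100% the error is higher at 332 than at 165. The bias stays fixed while the interval narrows, so the added sources or longer study period offered in section 9.4 would not cure it.

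**The case against.** A reader might infer that the error rate is in fact well above 2.5%. The documents do not support that. They give no PPV for the three sources; at PPV 95% the figure is 2.6–3.4% at 10% uptake and 2.0–2.7% at 5% uptake, and the larger figures need a PPV that the documents neither support nor exclude. Section 9.9 is also conditional: it expects attenuation only under non-differential error. These points stand, and the claim has to be conditional.

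It can also be said that 2.5 and the one-sided alpha belong to the sample-size material, while sections 9.7.1 and 9.7.2 plan estimates with 95% intervals and no test against 2.5. That is right as far as it goes. However, checklist item 2.1.4 points to sections 8.1 and 9.5 for the hypotheses to be tested, so a comparison of the pooled bound with 2.5 is plainly intended.

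Code lists and bias-analysis detail are deferred to the SAP, which might add an outcome analysis. That would not make the checklist's reference to 9.7.5 correct.

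Finally, a correction may not be possible centrally. Table 11 expects 7 exposed MCM events in Carelon and 8 in France, below the masking limits of 10 and 11 in section 9.7, and section 9.6 says individual-level Carelon data stay with the provider. Pooling uses PS-adjusted RRs, so correcting a crude 2×2 table is not enough. This stands and shapes the fix.

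**Conclusion.** The point holds in conditional form. The 2.5 threshold is judged on codes taken as true MCM. The bias that section 9.9 regards as likely under non-differential error favours ruling out harm, the protocol does not say so, and nothing in 9.7.5 examines it: the bias analysis is for confounding, and MACDP re-classifies the same recorded diagnoses. Checklist item 10.6 is therefore wrong as it stands.

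At 10% uptake and 1:2, the error against a true RR of 2.5 is at or near the nominal 2.5% while PPV is about 95% or more, is 3.9–5.0% at 90%, and reaches 15–18% at 70%. At 5% uptake the 70% figure is 7.6–9.5%. All of this rests on the assumed PPV range, non-differential error and a coded comparator risk of 7%. It is not evidence that the codes in these sources are poor.

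**What to change.** - Extend the quantitative bias analysis in 9.7.5 to MCM outcome misclassification. Run it within each data source, because of masking and access limits, and in a form compatible with the PS-adjusted RR.
- Re-pool and report, as a sensitivity analysis, the corrected upper bound over a pre-set PPV range, together with the lowest PPV at which 2.5 remains excluded.
- State in 9.9 that bias towards the null favours the safety conclusion.
- Correct the answer or the reference at checklist item 10.6.

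Exclusion of 2.5 across the whole PPV range should not become a condition for the main conclusion. Requiring it down to PPV 70% is roughly the same as moving the margin to 2.03. At 1:2 (Poisson form) that cuts power from 96% to 79% at 10% uptake, and from 66% to 39% at 5%.

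The cost is some extra programming in each source and a corrected bound that will look less favourable. With so few exposed events per source, the corrected estimates will also be imprecise.
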